## **OBJECTIVES AND HYPOTHESIS**

The objective of this study is to analyse the effectiveness of the MSC program versus the CBT program in order to improve self-care, compassionate relation to oneself, quality of life in a chronic pain patient’s sample. Both treatments are conducted in groups, are psychotherapeutic oriented, both have an 8 weeks duration, weekly frequency, 2 and a half hours per session.

The principal hypothesis of this investigation is:

- MSC program will be, at least, as effective as the CBT program in order to improve self-care capacity and self-compassion in chronic pain patients (decreasing self-criticism, isolation feelings, and thoughts over-identification) at the post-treatment time and in a 6-months follow-up.

Secondary hypothesis:

- MSC program will be, at least, as effective as CBT program in order to improve quality of life, and acceptance capacity; and as effective as CBT to reduce catastrophizing, daily life interference, anxiety and depression in a chronic pain patients simple, at the post-treatment time and a 6 months follow-up.

- We also hypothesize that MSC program will be, at least, as effective as CBT program in order to maintain the achieved benefits in a 6 months follow-up.

- Treatment satisfaction will be higher in MSC program, being treatment adherence higher in this program than in CBT program.

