## **METHODS**

We wrote a investigation protocol which has already been approved by the Research Ethics Committee of Hospital Universitario La Paz, Madrid.

This is a prospective experimental study; blind randomized, with parallel groups and final blind analysis with, at least, 64 patients with chronic pain.

All patients will be assessed at the pre-intervention moment, at the post-intervention moment (8 weeks), and in a 6 months follow-up.

This is a pre-post experimental design with which we intend to compare the effectiveness of 2 psychotherapeutic treatments for chronic pain. The two arms of treatment of this Randomized Clinical Trial are:

a) Mindful Self-Compassion Program (MSC)

b) Cognitive-Behavioural Program for chronic pain (CBT).

Both treatments are conducted by experimented clinicians with wide experience in chronic pain. We will conduct 8 therapeutic groups in total (4 for each arm treatment), with approximately 15 people per group.

We have estimated that we need a N=64 in order to detect significant differences in the principal outcome (self-care and self-compassion) with a size effect=0.5, SD=0.6, alpha=0.05 and power=90%.

During the investigation we will create a Data Base in accordance with current regulations. Data will be use following the principles contained in the Organic Law 15/1999, 13th December, of Personal Data Protection. All data will be electronically introduced in this database and data analysis will be conducted using SPSS 18.0.

It will be conducted an exploratory study of all variables previous to statistical analysis in order to identify anomalous data.

It has been done a first-step approximation to the behaviour and variability of the main outcome of the study with a 30 patients simple randomized to both arms in order to estimate the necessary N of the study.

Descriptive analysis of qualitative variables will be expressed in terms of frequencies and percentage, and analysis of quantitative variables will be expressed in terms of mean, standard deviation, median and interquartile range. The analysis will be conducted by intention to treat. Comparison of qualitative variables between groups of interventions or between segmentation factors will be conducted with Fisher test. We will apply t-Student, Mann-Whitney, ANOVA or Kruskal-Wallis test in quantitative variables, depending on the normality of the variable (tested with Kolmogorov-Smirnov-Lilliefords test) and the number of compared categories..

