Analysis of the changes along the treatment on principal and secondary outcomes of effectiveness will be conducted through a General Lineal Model (ANOVA with repeated measures), which allows checking if there are statistical significant differences in these changes based on arm of intervention.

Regression models will be conducted in order to identify prognostic factors.

Variables "Treatment satisfaction" and "adherence to treatment" will be compared using t-Student test for independent samples for patients who complete the treatment.

Aetiology of chronic pain will be taken into account when it is known.

Given the shortage of studies until the date referred to the effects of interventions based on self-compassion in chronic pain patients, the results of this study may give empirical date about the effectiveness and the need of mindful-self-compassion-based interventions, integrated in a multidisciplinary, approach to improve quality of life and self care in chronic pain patients.

Now, we go on to describe the two arms of treatment tested in this study:

- Mindfulness Self-Compassion (MSC) is a standardized program to increase self-compassion. It has been developed by Neff and Germer. The structure of the program is similar to de Mindfulness-Based Stress Reduction program (MBSR), with duration of sessions between 2 and 2 hours and a half. The frequency of the sessions is one per week for 8 weeks, with practical and experiential exercises in sessions and between sessions. The MSC program focuses primary on helping patients to develop self-compassion, and it includes Mindfulness just as a secondary component. The MSC program will be conducted by a clinician trained in this specific program.

- CBT: It has been adapted a Cognitive-Behavioural Intervention for Chronic Pain by Moix and Kovacs. Our program will have 8 sessions, with duration of sessions between 2 and 2 hours and a half. The frequency of the sessions is one per week for 8 weeks, with homework between sessions. During these 8 sessions we will train the following techniques: psycho-education about pain, relaxation training, cognitive restructuring training, solving problem training, psycho-education about emotions, interpersonal skills and time organization.

There we present the variables of the study:

Primary Outcome Measure:

- Self-Compassion: Self-Compassion Scale (SCS, long version). Self-compassion and Self-care. Self-kindness, Common Humanity and Mindfulness.

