[Time Frame: At the beginning of the intervention, at the end of the intervention and at a 6 months follow-up]

Secondary Outcome Measures:

- Acceptance: Chronic Pain Acceptance Questionnaire (CPAQ). Activity engagement, Pain

willingness. [Time Frame: At the beginning of the intervention, at the end of the intervention and at a 6 months follow-up]

- Pain Interference: Pain interference in daily life. Brief Pain Inventory (BPI): pain intensity and impact of pain in daily life. [Time Frame: At the beginning of the intervention, at the end of the intervention and at a 6 months follow-up]

- Pain Intensity: Analogical Visual Scale.[Time Frame: At the beginning of the intervention, at the end of the intervention and at a 6 months follow-up]

- Catastrophising: Pain Catastrophising Scale (PCS). Rumination, magnification of consequences and hopelessness [Time Frame: At the beginning of the intervention, at the end of the intervention and at a 6 months follow-up]

- Quality of life: SF-36. Physical function, physical role, body pain, general state of health, vitality, social function, emotional role and mental health.[Time Frame: At the beginning of the intervention, at the end of the intervention and at a 6 months follow-up]

- Anxiety and Depression Levels of anxiety and depression. Symptomatology. Hospital Anxiety and Depression Scale (HADS). [Time Frame: At the beginning of the intervention, at the end of the intervention and at a 6 months follow-up]

- Satisfaction with the treatment Satisfaction with the treatment (CRES-4) [Time Frame: At the end of the intervention]

- Adherence to the treatment Adherence to the treatment (Number of sessions that one patient attends) [Time Frame: At the end of the intervention]

Other Pre-specified Outcome Measures:

- Socio-demographic Data: Age, gender, marital status, family life, job status, time with pain, type of pain, psychiatric history, course pain expectation, number of visits to emergency units in the last 3 months, number of visited doctors in the last 3 months. [Time Frame: At the beginning of the intervention]

Inclusion and exclusion criteria are as follow:

- Inclusion Criteria:
  - Older than 18 years old.
  - Being in treatment in the Chronic Pain Unit at Hospital Universitario La Paz because of having a chronic pain of more than 3 months of duration, no matter the aetiology.
  - Capable of understanding and giving his or her written informed consent.

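### Satisfaction (CRES-4) is compared only in patients who complete treatment, against the plan's intention-to-treat rule; if dissatisfied patients leave the arms unequally, the arm that loses more of them looks better

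*Combined protocol and SAP*

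**What the plan says.** All references are to the combined protocol and SAP.

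- **Hypothesis** (OBJECTIVES AND HYPOTHESIS, last secondary hypothesis): "Treatment satisfaction will be higher in MSC program, being treatment adherence higher in this program than in CBT program". It concerns the programmes and is not limited to completers.
- **Measurement** (METHODS, secondary outcome measures): "Satisfaction with the treatment (CRES-4) [Time Frame: At the end of the intervention". This is a single time point. The entry does not say whether patients who stop early are asked.
- **Assessment schedule** (METHODS, opening paragraphs): "All patients will be assessed at the pre-intervention moment, at the post-intervention moment (8 weeks), and in a 6 months follow-up".
- **General analysis rule** (METHODS, statistical paragraphs): "The analysis will be conducted by intention to treat".
- **Test for this endpoint** (METHODS, after the repeated-measures paragraph): "Variables 'Treatment satisfaction' and 'adherence to treatment' will be compared using t-Student test for independent samples for patients who complete the treatment".

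Completion is not defined. No dropout rate, missing-data rule or sensitivity analysis is given for satisfaction.

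**The concern.** Completing treatment happens after randomisation, and how satisfied a patient is plausibly affects it. Restricting the test to completers therefore selects patients on something close to the outcome itself. Where dissatisfied patients leave, the low scores go with them and the mean of the remaining patients rises. If one arm loses more such patients, its mean rises more.

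Two errors could follow. If MSC patients really are more satisfied and CBT loses more of its dissatisfied patients, the planned test understates the difference the trial set out to show. If there is no true difference, the arm with more loss can appear better. In both cases the result describes those who stayed, whereas the hypothesis is about the arms as randomised.

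**Working it through.** **1. The plan's own figure.** The only sample-size figure is N=64, for the primary outcome (difference 0.5, SD 0.6, alpha 0.05, power 90%). Two-sided, normal approximation: n per arm = 2 × (1.960 + 1.282)² × 0.6² / 0.5² = 30.3, so 31 per arm and 62 in total. The exact t calculation gives 32 per arm, 64 in total, with power 90.7%. The figure reproduces. It says nothing about satisfaction and is used here only to set 32 per arm.

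**2. Direction of the bias.** Let a proportion p of an arm stop, with satisfaction g SD below that of completers. The arm mean is then the completer mean minus p × g, so the completer mean is too high by p × g. With dropout p1 and p2 and the same g in both arms:

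bias = g × (p1 − p2) SD, in favour of the arm with dropout p1.

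It is zero if g = 0 or p1 = p2.

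**3. A worked case (assumed values).** Take g = 1 SD, dropout 30% against 10%, 32 randomised per arm and no true difference.
- Bias = 1 × (0.30 − 0.10) = 0.20 SD.
- Completers: 32 × 0.70 = 22.4 and 32 × 0.90 = 28.8. SE = √(1/22.4 + 1/28.8) = 0.282 SD.
- Two-sided rejection rate = Φ(0.20/0.282 − 1.96) + Φ(−0.20/0.282 − 1.96) = 10.9%.

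With g = 0.5 SD the bias is 0.10 SD and the rejection rate 6.5%. With g = 1.5 SD they are 0.30 SD and 18.7%. A larger trial does not dilute the bias. METHODS plans 4 groups of about 15 per arm; at 60 per arm the three rates become 7.7%, 16.3% and 30.8%.

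**4. Simulation with a graded link (assumed values).** There are 32 patients per arm, satisfaction is normal with SD 1, and dropout probability is expit(a − b × satisfaction), with a set in each arm to give the stated dropout. The odds of dropping out rise by exp(b) per SD of lower satisfaction: 1.6-fold for b = 0.5, 2.7-fold for b = 1, 7.4-fold for b = 2. Those who stop are then about 0.5, 0.85 and 1.3 SD less satisfied than completers. The test is a two-sample t-test at 5% in completers. Bias is 0.50 minus the completer difference. Because a is set separately in each arm, the same shift applies when there is no true difference.

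| Rise in dropout odds per SD | Dropout MSC / CBT | Completer difference when truth is 0.50 SD | Bias towards CBT | Type I error, no true difference |
|---|---|---|---|---|
| 1.6-fold | 10% / 20% | 0.45 | 0.05 | 5.4% |
| 1.6-fold | 10% / 30% | 0.41 | 0.09 | 6.2% |
| 2.7-fold | 10% / 20% | 0.42 | 0.08 | 6.1% |
| 2.7-fold | 10% / 30% | 0.34 | 0.16 | 8.9% |
| 7.4-fold | 10% / 20% | 0.38 | 0.12 | 7.5% |
| 7.4-fold | 10% / 30% | 0.27 | 0.23 | 14.5% |

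With 20% dropout in both arms the completer difference stays at 0.50 and the type I error at 5%, even with the strongest link.

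**5. Power, with the two causes separated.** For a true 0.5 SD difference, power with every patient scored is 50%. If dropout is unrelated to satisfaction, power falls to 44% (10%/20%) or 41% (10%/30%) simply because there are fewer patients. With the 2.7- to 7.4-fold links it falls to 35–34% and 23–18%. Only the drop below 44% or 41% is due to selection.

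**The case against.** **Patients who stop may well be scored.** A reader might infer that they never receive a CRES-4 score and that the loss cannot be repaired at analysis. The documents do not support this. METHODS has all patients assessed at 8 weeks, CRES-4 is scheduled at the end of the intervention, and its entry is not limited to completers. The completer restriction is on the analysis. What stands is that collection from those who stop is not made explicit, and that the test omits them even if they are scored.

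**The plan does not predict unequal dropout.** It would be easy to read the adherence hypothesis that way. But adherence is defined as "Adherence to the treatment (Number of sessions that one patient attends", and completion is undefined, so fewer sessions need not mean more non-completers. This objection stands: unequal loss is a possibility, not something the plan states.

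**The bias is conditional and may be small.** This also stands. With the weakest link examined, it is 0.05 to 0.09 SD and the type I error about 6%.

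**If CBT loses more, the error works against the trial's own hypothesis.** True: an MSC advantage is then diluted, and false positives mostly favour CBT. If MSC loses more, the direction reverses. The plan provides no analysis that would show which case applies.

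**A completer comparison is a legitimate, narrower question, stated in advance.** It is legitimate, but it is not the question in the hypothesis, and the plan neither labels it as narrower nor reconciles it with the intention-to-treat rule.

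**Conclusion.** The point holds in conditional form. The plan states a completer-only rule for satisfaction that conflicts with its intention-to-treat statement and does not match its hypothesis. The rule gives a biased comparison if patients who stop are less satisfied than completers and the arms lose them unequally. To call the comparison biased outright would go further than the documents allow.

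The size cannot be computed from the plan. Under the simulated assumptions (32 per arm, 10% against 20–30% dropout, dropout odds rising 1.6- to 7.4-fold per SD of lower satisfaction), the bias is about 0.05 to 0.23 SD. The type I error is then 5.4% to 14.5%, and a true 0.50 SD MSC advantage appears as 0.45 to 0.27 SD if CBT loses more.

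The change should be made, but this is a secondary endpoint. The primary analysis and N=64 are untouched. The same sentence also governs adherence, which is outside this point.

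**What to change.** 1. In the METHODS sentence that sets the test, for satisfaction, replace the restriction to completers with: *for all randomised patients with a CRES-4 score, in the arm allocated*.
2. In the secondary outcome list, state that CRES-4 is sought at the planned 8-week assessment from all patients, including those who stopped early.
3. Report the number without a CRES-4 score in each arm.
4. Add one sensitivity analysis: a rank test in which patients who stopped and have no score take the lowest rank. It is needed because patients with a score are still a subset formed after randomisation.
5. Keep the completer comparison as descriptive, and define completion.

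**Cost.** Wording changes in two places, and one short questionnaire, already in use, given at an assessment already planned for all patients. No extra patients are needed. Some who stop will not reply, and the observed difference may be noisier.

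### Adherence is compared only in patients who complete treatment, an undefined set selected on attendance itself, so the adherence hypothesis is not tested in the randomized arms

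*Combined protocol and SAP*

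**What the plan says.** The last secondary hypothesis in Objectives and Hypothesis reads: "Treatment satisfaction will be higher in MSC program, being treatment adherence higher in this program than in CBT program". It is worded for the two programs and is not limited to those who finish them.

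The list of secondary outcomes in Methods defines the variable as "Adherence to the treatment (Number of sessions that one patient attends", taken at the end of the intervention. For CBT, Methods states "Our program will have 8 sessions"; for MSC, "The frequency of the sessions is one per week for 8 weeks, with practical and experiential exercises in sessions and between sessions". The count therefore runs from 0 to 8 in both arms.

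The analysis part of Methods has a general rule, "The analysis will be conducted by intention to treat", and a specific rule for satisfaction and adherence: these "will be compared using t-Student test for independent samples for patients who complete the treatment". That is the only comparison specific to adherence. No section says what completing the treatment means, and no reason is given for leaving the intention-to-treat rule.

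**The concern.** Completion is known only after randomization and, for this outcome, it is the outcome or close to it. Whether completion means a minimum number of sessions or not dropping out, the patients with the poorest adherence are removed first, and adherence is then compared among the rest. The two remaining sets need not be comparable, because different kinds of patients may stay in each arm.

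The planned test could therefore miss a real difference in drop-out between the programs, show a larger difference than exists in the randomized arms, or favour the wrong program. Because the set is undefined, the plan does not even fix which of several completers-only questions will be answered.

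**Working it through.** **The plan's own figure.** The documents size the trial for self-compassion only: difference 0.5, SD 0.6, two-sided alpha 0.05 (sidedness assumed), power 90%. The t-based calculation gives 31.25, rounded up to 32 per arm, or 64 in total, which matches the plan. It does not bear on adherence, for which no figure is given.

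**Limiting case.** If completion means all 8 sessions, every completer scores 8, the variance is zero and a t-test cannot be computed.

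**Model for other readings.** All rates are assumptions. A patient drops out with probability d before each of 8 sessions; a patient still in treatment misses a session with probability m.

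- Mean sessions, all randomized: (1 - m) × Σ (1 - d)^w, w = 1 to 8.
- Mean among those who never drop out: 8 × (1 - m).
- With a cut-off c: Σ x·P(x) / Σ P(x) over x ≥ c. Here P(x) mixes binomial(k, 1 - m) over the number of sessions k reached before drop-out. P(k) = (1 - d)^k × d for k < 8, and (1 - d)^8 for k = 8.

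**Scenario D, arms differ in drop-out** (d 2% MSC, 8% CBT; m 10% in both):
- All randomized: 0.90 × 7.313 = 6.581 and 0.90 × 5.598 = 5.038; difference 1.543.
- At least 4 sessions (91% and 69% of patients): 7.062 - 6.669 = 0.393.
- Not dropped out: 8 × 0.90 = 7.2 in both arms; difference 0.

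**Scenario M, arms differ in missed sessions** (d 4% in both; m 5% MSC, 20% CBT):
- All randomized: 0.95 × 6.687 = 6.352 and 0.80 × 6.687 = 5.349; difference 1.003.
- Not dropped out: 8 × (0.20 - 0.05) = 1.200.

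**Scenario R, mixed patients** (half regular: d 2%, m 5% in both arms; half irregular: m 35%, d 4% MSC, 20% CBT):
- All randomized, regular half: 0.95 × 7.313 = 6.947 in both arms.
- All randomized, irregular half: 0.65 × 6.687 = 4.346 (MSC) and 0.65 × 3.329 = 2.164 (CBT).
- Arm means 5.647 and 4.555; difference 1.091.
- Not dropped out: regular patients (85% stay) average 7.6 sessions. Irregular patients average 5.2, but 72% of them stay in MSC and 17% in CBT. The means are 6.499 and 7.205; difference -0.706. CBT looks better because it has lost its irregular attenders.

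Differences in mean sessions, MSC minus CBT:

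| Set compared | D | M | R |
|---|---|---|---|
| All randomized | 1.54 | 1.00 | 1.09 |
| At least 4 sessions | 0.39 | 1.01 | -0.36 |
| At least 5 | 0.21 | 0.94 | -0.34 |
| At least 6 | 0.08 | 0.72 | -0.19 |
| Not dropped out | 0 | 1.20 | -0.71 |
| At 8-week assessment, 25% of drop-outs attending | 0.68 | 1.14 | 0.09 |
| At 8-week assessment, 75% of drop-outs attending | 1.36 | 1.04 | 0.88 |

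The last two rows assume that everyone still in treatment attends the assessment.

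**Rejection rates.** Patient-level t-test, two-sided 0.05, 20,000 simulated trials per cell, at 32 per arm (the minimum of 64, 1:1 assumed) and 60 per arm (4 groups of about 15):

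| Set compared | D, 32 / 60 | M, 32 / 60 | R, 32 / 60 |
|---|---|---|---|
| All randomized | 74% / 95% | 42% / 66% | 34% / 58% |
| At least 4 sessions | 23% / 38% | 88% / 99% | not shown |
| Not dropped out | 5% / 5% | 99% / 100% | 32% / 56%, essentially all for CBT |

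These rates treat patients as independent. Both programs are delivered in groups, so the all-randomized power would be lower once clustering is allowed for; the point does not depend on that.

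**The case against.** The strongest reply is that Methods already promises intention to treat and gives unrestricted between-arm tests for quantitative variables, so an all-randomized comparison of session counts exists on paper. It does, but the specific sentence on adherence contradicts it. An analyst would follow the specific sentence, and at the least the two must be reconciled.

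Second, completion may mean reaching the post-treatment assessment, since Methods says "All patients will be assessed at the pre-intervention moment, at the post-intervention moment (8 weeks), and in a 6 months follow-up". Low attenders are then not necessarily excluded, and the distortion is milder: in R the sign no longer reverses. This stands as a possible reading, but the documents do not state it, and the set is still selected unless everyone attends.

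Third, the hypothesis does not name its population, and attendance among those who stay is a legitimate question. That is fair, but it is a narrower question, and a claim that one program has higher adherence than another is naturally read as including those who leave.

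Fourth, all rates are assumed, R is built to show that reversal is possible, and the all-8-sessions reading is unlikely to be what was meant. All three points stand. The numbers show what can happen, not what will; the mismatch itself follows from the text.

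Finally, Methods promises a "final blind analysis with, at least, 64 patients with chronic pain". Blinding makes it harder to choose a cut-off that favours one arm. It neither defines the set nor removes the selection.

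**Conclusion.** The concern holds. As written, the adherence hypothesis has no matching adherence-specific test: the planned comparison uses an undefined set formed after randomization on the outcome or close to it. That conclusion needs no assumed rates.

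The size does. Under the rates shown, the completers-only difference can be close to zero, about right, too large or of the wrong sign, so no direction of bias is claimed. The reach is one secondary outcome. The plan should be corrected, but the primary analysis is unaffected.

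Restricting satisfaction (CRES-4) to completers is easier to understand, because patients who left may have no score; that result is simply conditional on staying.

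**What to change.** In the analysis part of Methods:

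1. Make the comparison of sessions attended (0 to 8, with 0 for those who never start) among all randomized patients the test of the adherence hypothesis. Report never-starters by arm. State in advance whether the t-test or the Mann-Whitney test applies, since the count may be skewed and Methods names both.
2. Define completing the treatment before the data are seen. As a supportive analysis, compare the proportion completing by arm with the Fisher test that Methods already names.
3. Label any completers-only session count as descriptive.
4. Describe the satisfaction result as conditional on staying, and give the CRES-4 return rate by arm.

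The cost is a change of wording and one definition. No imputation is needed provided attendance is recorded for patients who drop out, which the documents do not state explicitly. There are two downsides. Scoring never-starters as 0 mixes uptake with adherence, hence the separate report. Where the arms differ only in missed sessions, the all-randomized test has less power than the completers test (42% against 88% at 32 per arm in scenario M, at least 4 sessions). The reason for the change is to match the hypothesis, not to gain power.

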  - Significant levels of distress and disability related to the pain at the beginning of treatment, assessed by clinical interview and HADS (> or = 8).
  - Significant levels of pain interference in daily life assessed by sub-scale of interference of the Brief Pain Inventory (> or = 5).
  - Significant levels of "catastrophising" at the beginning of the treatment assessed by Pain Catastrophising Scale (PCS) (> or = 30).
  - Patients that meet criteria for Mixed Adaptive Disorder, mild to moderate Depressive Disorder or Dysthymia, assessed by clinical interview conducted by a psychiatry of the Chronic Pain Unit or Mental Health Centre.
- Exclusion Criteria:
  - Intellectual disability or cognitive impairment or dementia.
  - Insufficient knowledge of the language to understand and participate on the intervention program.

- Serious mental illness in acute state at the moment of the beginning of the intervention.
- Substance abuse in the last 6 months.
- Autolytic ideas at the moment of the assessment.
- Previous training in mindfulness or CBT techniques.

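### Parity with CBT on self-compassion, or improvement within the arms, cannot show that MSC is effective or needed; on the primary scale only superiority over CBT can support an effectiveness claim

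*Combined protocol and SAP*

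**What the plan says.** The formal objective is comparative: to "analyse the effectiveness of the MSC program versus the CBT program" (OBJECTIVES AND HYPOTHESIS). The principal hypothesis is that "MSC program will be, at least, as effective as the CBT program in order to improve self-care capacity and self-compassion", after treatment and at 6 months. The secondary hypotheses use the same form for quality of life, acceptance, catastrophising, interference, anxiety and depression, and for maintenance of benefit.

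METHODS describes two active arms and no untreated, waiting-list or usual-care arm. It opens with "This is a pre-post experimental design" and says that "we intend to compare the effectiveness of 2 psychotherapeutic treatments for chronic pain". The main analysis is a repeated-measures ANOVA that tests whether change differs by arm. The same section closes its analysis text with the hope that "the results of this study may give empirical date about the effectiveness and the need of mindful-self-compassion-based interventions".

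The primary outcome is the SCS. Entry requires HADS of at least 8, a PCS score of at least 30, and significant interference, "assessed by sub-scale of interference of the Brief Pain Inventory (> or = 5"). The same three instruments are listed as secondary outcomes at the start of the intervention, at its end and at 6 months.

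**The concern.** With two active arms, a trial can speak to absolute benefit in only two ways: by matching a comparator known to work on the outcome in question, or by change from baseline.

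The first route fails on the primary scale. SCIENTIFIC BACKGROUND credits CBT with benefit across many outcome measures, but it does not mention self-compassion in that context. The CBT techniques listed in METHODS contain no self-compassion component. The second route is weak because patients are selected for high scores on three of the scales later used as outcomes.

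If the plan does not say which results may support which conclusion, a finding of no difference on the SCS, together with improvement in both arms, could be reported as evidence that MSC works and is needed. Neither part of that result would show it.

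**Working it through.** **1. What the sample size was computed for.** Inputs from METHODS: difference 0.5, SD 0.6, alpha 0.05, power 90%. Equal allocation is assumed from four groups per arm.

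Normal approximation, two-sided: n per arm = 2(1.960 + 1.282)² × 0.6² / 0.5² = 2 × 10.507 × 1.44 = 30.3, so 31 per arm and 62 in total. The two-sample t version gives 31.25, so 32 per arm and **64 in total**, with power 90.7%. The stated figure is therefore reproduced as a two-sided test that the arms differ on the primary scale. It addresses neither a comparison with no treatment nor parity.

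**2. What parity on the SCS would show.**
- If CBT raises self-compassion, parity suggests that MSC does too.
- If CBT does not raise it, parity means that MSC does not either.
- The document gives no basis for choosing between these.

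A margin does not help. Take an assumed margin of 0.5 points with one-sided 0.025, SD 0.6 and a true difference of zero. The formula is then the same as in step 1: 62 patients for 90% power. So if neither programme moved the SCS at all, 64 patients would still show MSC non-inferior to CBT in about 90% of trials. The margin is illustrative, as the plan gives none. A tighter margin needs more patients (170 in total for 0.3, 380 for 0.2), but the logic is unchanged.

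**3. What change from baseline would show on the three entry scales.** For a normally distributed score selected above a cut-off c (in SD from the clinic mean) with retest correlation r and no treatment effect, the expected improvement is (1 − r) × φ(c) / (1 − Φ(c)). The document gives no clinic mean, SD or retest correlation, so c and r are assumptions. The selection term is 0.3521/0.6915 = 0.509 at c = −0.5, 0.3989/0.5 = 0.798 at c = 0, and 0.3521/0.3085 = 1.141 at c = +0.5.

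| Cut-off c | r = 0.8 | r = 0.7 | r = 0.6 |
|---|---|---|---|
| 0.5 SD below mean | 0.10 SD | 0.15 SD | 0.20 SD |
| at the mean | 0.16 SD | 0.24 SD | 0.32 SD |
| 0.5 SD above mean | 0.23 SD | 0.34 SD | 0.46 SD |

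The formula treats each scale alone and assumes that the qualifying score also serves as baseline. With both arms pooled (64 patients), the chance of a significant improvement over time from this source alone runs from about 26% (c = −0.5, r = 0.8) to 99% (c = +0.5, r = 0.6). This uses SD of change = √[(1 − r)²v + 1 − r²], where v is the variance of the selected scores (0.486 and 0.268 at those two cut-offs). The SD of change is then 0.616 and 0.826, and the chance is Φ(8 × shift / SD − 1.96).

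**4. Where this does not apply.** The SCS is not an entry criterion, so step 3 does not act on it directly. Randomisation exposes both arms to the same selection, so the MSC–CBT difference is free of this bias on every scale.

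**The case against.** The strongest reply is that the plan commits to no absolute claim. The sentence about effectiveness and need is hedged and sits in a closing rationale. The objective, the design statement and the ANOVA are all comparative, and no passage makes a within-arm test evidence of efficacy. Comparing with an established therapy is also a legitimate design. All of this stands, and it limits the point to what may be concluded. It does not remove the point: the principal hypothesis itself is framed as parity on a scale where the comparator's effect is undocumented, and nothing bars use of the time effect.

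Three stronger readings are tempting and are not supported:

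- A reader might infer that regression to the mean will inflate the primary outcome. The SCS is not selected on, and is affected at most indirectly, through spontaneous or non-specific change.
- A reader might infer that both arms are sure to improve substantially on the entry scales. The size is unknown. In a specialist pain unit a cut-off may lie below the clinic mean, and the full effect requires the screening score to double as baseline. The HADS and PCS criteria are dated to the start of treatment, but the BPI criterion carries no date.
- A reader might note that, with no true difference, MSC would fail to be significantly worse in 97.5% of trials and treat this as an error rate. It is 1 − 0.05/2 for any two-sided 5% test, and in that scenario MSC really is no worse.

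The background does report that MSC improved self-compassion, but in a non-clinical population. That makes a wholly inert MSC less plausible without establishing an effect in these patients.

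**Conclusion.** The concern holds as a limit on inference. Parity with CBT on the SCS cannot show that MSC is effective, because the document gives no evidence that CBT moves that scale, and a margin alone does not repair this. Need does not follow from parity on any outcome: if CBT does as well, MSC has not been shown to be needed. Within-arm change is not a substitute. On HADS, BPI interference and PCS it includes an unknown regression effect, about 0.1 to 0.46 SD under the stated assumptions (r from 0.6 to 0.8, cut-off from 0.5 SD below to 0.5 SD above the clinic mean).

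A reader might go further and call the trial invalid for want of an untreated arm. The document does not support that: the randomised MSC–CBT contrast is sound against this bias, and a demonstrated MSC advantage would be informative.

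**What to change.** Amend OBJECTIVES AND HYPOTHESIS and the closing rationale in METHODS as follows.

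1. Limit conclusions to MSC relative to CBT.
2. Claim effectiveness on self-compassion only if MSC is superior to CBT on the SCS in the between-arm comparison. This matches the existing sample size and the planned ANOVA.
3. State that within-arm change and the ANOVA time effect will not be used as evidence of effectiveness.
4. Remove the reference to need.
5. Where parity wording is kept for secondary outcomes, judge it by a confidence interval against a justified margin, present it as relative to CBT only, and do not treat it as proof of absolute benefit. This matters most at 6 months, because SCIENTIFIC BACKGROUND says that much of the benefit of CBT is not maintained in the long term.

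The cost is a less favourable permitted conclusion: a null result on the SCS would leave open whether either programme works on that scale. No new arm or patients are needed for the wording change. Whether 64 patients suffice for a secondary margin depends on the margin chosen.
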